--	---

	
absence of confirmed renal responses, will be examined using the Mantel-Haenszel test. In order to determine whether the QOL measures reflect contributions that were independent of or equivalent to those made by treatment assignment, presence or absence of confirmed renal responses, or clinical characteristics, stepwise proportional hazards regression with the significance level for entry into and for staying in the model set at 5% will be used to identify clinical and health status factors related to changes in QOL measures from the beginning to the end of treatment.
 
Renal Biopsy Scoring
 
Results of renal biopsy scoring will be recorded in a central REDCap data bank (ARC). Renal biopsies will be scored by a predefined set of criteria for the degree and pattern of amyloid involvement and distribution. The renal pathology group will use established criteria and perform the scoring using a standard operating procedure and data sheet (Appendix 8). Comparisons will be made between the NEOD001 and placebo groups by the CMH test stratified by the pre-randomization stratification factors at alpha of 0.05.
 
Transcriptional Profiles
 
Renal biopsy sections for transcriptional profiling will be processed following the standard operating procedures of The Nephrotic Syndrome Study Network (“NEPTUNE”). NEPTUNE is an integrated group of academic medical centers, patient support organizations and clinical research resources dedicated to advancing the understanding and treatment of certain kidney diseases unrelated to dysproteinemias. The tissue processing, microarray and bioinformatics work for the RAIN trial will be performed by the principal investigators of NEPTUNE at the University of Michigan in Ann Arbor (Appendix 10).

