The primary endpoint is the confirmed renal response rate at 13 months after initiating therapy (after 12 months of NEOD001 or placebo). Renal response is measured according to criteria that have been developed and validated in two large European cohorts, employing eGFR and 24-hour proteinuria. A renal response is a  $\geq 30\%$  decrease in proteinuria or drop of proteinuria below 0.5 g/24h in the absence of renal progression. Renal progression is defined as  $\geq 25\%$  decrease in eGFR. A confirmed renal response is one that has been documented as present at both 12 and 13 months after initiating therapy. Secondary end-points of this trial involve comparisons of measured GFR (mGFR) compared to eGFR at study entry, and comparisons of patients who receive NEOD001 or placebo with respect to time to CKD 4 or 5 status, time to eGFR  $\leq 15$  or dialysis, time to doubling of serum creatinine, time to a  $\geq 40\%$  reduction in eGFR, and rates of renal response and progression at 26 months after study entry in patients with maintained hematologic responses. We will also assess safety and tolerability of NEOD001 and mortality due to all causes at 26 months.

In this multicenter trial, we plan to treat AL patients who are greater than 18 years old and have had hematologic responses to their last prior therapy and who have persistent AL renal involvement with renal stage 1, 2 or 3 disease. Patients must be chronic kidney disease stage (CKD)  $\leq 3$ . Patients with NT-proBNP  $\geq 1800$  are not eligible for this trial. Patients must have prior confirmed AL amyloidosis based on Congo red and immunohistochemical staining or mass spectrometry typing of a tissue biopsy (excluding bone marrow), and patients screened and found otherwise eligible must have a screening renal biopsy to confirm that amyloidosis is the cause of renal disease before being declared eligible for RAIN. Eligible patients are then stratified based on response to prior therapy (CR/VGPR vs PR) and renal stage (stages 1 or 2 vs stage 3) and randomized.

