#### **3.2.3 Ancillary Studies**

Ancillary studies for this trial are being performed in collaboration with the Amyloidosis Research Consortium (ARC; described in synopsis). ARC will maintain ancillary study data in a REDCap database that the Tufts Neely Center for Clinical Cancer Research will create and oversee. The ancillary studies are being performed by a collaborative of Tufts, the ARC and for the gene expression work the University of Michigan. This work is being conducted under CDA and with IP agreements and carve-outs currently being negotiated. Patients will be assigned alphanumeric characters (absent all personal identifying information) that are linked to the Case

Report Forms maintained in REDCap by the participating centers and the Tufts Neely Center for Clinical Cancer Research.

The ancillary studies are designed in order to determine if there are differences among patients who receive NEOD001 and those who do not, and to define and identify differences among patients who have renal responses and those who do not, and renal progression or not, whether or not those patients receive NEOD001.

- Patient reported outcomes: Patients who receive NEOD001 or have renal responses or renal progression may experience changes in their quality of life. Patient reporting of outcomes is very important to in order to answer whether changes in renal disease status are associated with changes in quality of life. We will obtain SF-36 surveys at study entry and at 3, 6, 9 and 12 month visits and at ETD or initial and confirmatory EOS visit (Appendix 7). Scores will be computed and comparisons made by norm-based scoring (User's Manual for the SF-36v2 Health Survey, Second Edition).

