### **8 STATISTICAL METHODS AND CONSIDERATIONS**

#### **8.1 Analysis Populations**

Primary efficacy analysis is based on patients who are randomized and receive treatment for 12 months with NEOD001 or placebo.

Analysis of secondary time-to-event and also safety endpoints will be based on intention-to-treat. All patients randomized and treated with NEOD001 or placebo will be included.

The following subject populations will be evaluated and used for presentation and analysis of the data:

1. The Intent-to-Treat Population will include all randomized subjects who receive any amount of study drug (NEOD001 or placebo). Treatment assignment will be based on the randomized treatment.
2. The Safety Population will include all subjects who received any amount of study drug (NEOD001 or placebo). The Safety Population will be the primary population used for safety analyses. Treatment assignment will be based on the treatment actually received. For example, in the event of randomization, dispensing, or treatment errors, subjects will be included in the treatment group based on the treatment that was received.

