### 8.3.3 Ancillary Studies Analyses

The ancillary studies analyses will be performed by the Amyloidosis Research Consortium (ARC) in collaboration with Tufts Medical Center and the other RAIN study centers. Original forms will be faxed or reported electronically to the ARC data manager for entry into the RAIN ancillary studies database. The ancillary studies database will be maintained by ARC personnel and be accessed by Tufts and ARC data managers. This database is part of the secure REDCap database that is used for this trial.

SF-36 surveys (Appendix 7) will be scored and recorded in a central REDCap data bank. The SF-36 assesses 8 scales of health status from which a physical component summary (PCS) and a mental component summary (MCS) are derived (User's Manual for the SF-36v2 Health Survey, Second Edition). Summary scores will be standardized so a score of 50 corresponds to the average for the US population. Baseline and follow-up SF-36 scores will be compared for each patient and with population norms using 1-sample t tests. Pearson correlations, t tests, Wilcoxon 2-sample tests, and Mantel-Haenszel tests will be used to describe the associations between various component scales and scores of the SF-36 and clinical and demographic characteristics of these patients. The relationship of improvement or worsening in the PCS or MCS to 12 months of treatment with NEOD001 or placebo, and also to the presence or absence of confirmed renal responses, will be examined using the Mantel-Haenszel test. In order to determine whether the QOL measures reflect contributions that were independent of or equivalent to those made by treatment assignment, presence or absence of confirmed renal responses, or clinical characteristics, stepwise proportional hazards regression with the significance level for entry into and for staying in the model set at 5% will be used to identify clinical and health status factors related to changes in QOL measures from the beginning to the end of treatment.

Renal biopsies will be scored by a predefined set of criteria for the degree and pattern of amyloid involvement and distribution (Appendix 8). The renal pathology group will use established criteria, perform the scoring using a standard operating procedure and record results in a central data bank. Comparisons will be made between the NEOD001 and placebo groups by the CMH test stratified by the pre-randomization stratification factors at alpha of 0.05.

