#### **8.5. Determination of Sample Size**

This stratified randomized double-blind phase 2b study has as its primary efficacy end-point the confirmed renal response rate at 13 months after initiating therapy and is designed to detect an absolute increase in the renal response rate of 30% (from 25% in those receiving placebo to 55% in those receiving NEOD001). For the primary efficacy endpoint, the assumed true rates for NEOD001 vs placebo are 55% and 25%, respectively. Based on a chi-squared statistic to evaluate the null hypothesis at the alpha=0.05 level of significance, and assuming an 18% drop-out rate for hematologic progression requiring chemotherapy, a total sample size of 82 subjects (41 in the placebo group, 41 in the NEOD001 group) will enable us to reject the null hypothesis that the response rates for subjects receiving NEOD001 and placebo are equal with probability (power) 0.8. With 50 patients receiving placebo and 50 patients receiving NEOD001, we expect to have at least 41 evaluable patients in each group.

Of note, we are estimating the renal response rate over time in the arm not receiving NEOD001. In the relapsed setting, patients receiving lenalidomide and dexamethasone had an 18% renal response rate at 6 and 12 months; an additional 18% responded by 18 months. In relapsed patients receiving cyclophosphamide, lenalidomide and dexamethasone, 19% had renal responses, while in a phase 1/2 trial in relapsed patients (N=70) treated with bortezomib, 29% had a renal response. In the initial therapy setting, patients with renal involvement who received cyclophosphamide, bortezomib and dexamethasone (CyBorD) had a 25% renal response rate. Post-ASCT with bortezomib-based consolidation, while 50% of renal patients respond by the end of the first year, an additional 20% of renal patients respond in the second year post-ASCT. While we do not know the mix of patients who will be screened and enrolled in this trial, it is reasonable to assume that one third will be post-SCT, one third post initial and one third post second-line therapy. Allowing for a 6 month interval after chemotherapy and a 12 month interval after SCT, the weighted average of the renal response rates in these groups is 22.3%. We have chosen a higher estimate (25%) as the confirmed renal response rate in this study in patients receiving placebo.

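### The only multivariable SF-36 analysis names proportional hazards regression for change in a continuous score, with no event, cut-off, time origin or censoring rule, so it cannot be run as written

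*Combined protocol and SAP*

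**What the plan says.** Section 8.3.3 of the protocol, repeated in the statistical part of the synopsis, sets out the SF-36 analyses. Scores are compared with baseline and with population norms by one-sample t tests. Associations with patient characteristics are described by Pearson correlations, t tests, Wilcoxon tests and Mantel-Haenszel tests. Improvement or worsening in PCS or MCS is related to treatment and to confirmed renal response by a Mantel-Haenszel test.

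One model then follows: "stepwise proportional hazards regression with the significance level for entry into and for staying in the model set at 5% will be used". Its purpose is to pick out clinical and health-status factors "related to changes in QOL measures from the beginning to the end of treatment".

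On the scale of the outcome, section 8.3.3 states: "Summary scores will be standardized so a score of 50 corresponds to the average for the US population". After the entry survey, section 3.2.3 schedules SF-36 "at 3, 6, 9 and 12 month visits and at ETD or initial and confirmatory EOS visit". The same section says patient reporting is needed to "answer whether changes in renal disease status are associated with changes in quality of life".

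**The concern.** The named method and the stated outcome belong to different kinds of analysis. Proportional hazards regression models the time until something happens. The sentence describes how far a score moves between two fixed points, and the outcome is on a continuous scale.

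This is the only SF-36 analysis meant to separate the parts played by treatment arm, renal response and clinical features. The other methods take one or two variables at a time. As written, the analyst must first change either the model or the outcome, and would choose after seeing the data among options that can give different answers. There is a second, smaller risk. With 5% rules for entry and retention and no term forced in, treatment arm could drop out of a model in a randomised trial.

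**Working it through.** The documents state no sample size, event count or power for the SF-36 analysis, so there is no figure to reproduce. The check sets what the model needs beside what the text supplies.

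1. **Outcome.** The sentence gives change "related to changes in QOL measures from the beginning to the end of treatment". That is a difference between two scores over an interval that the design fixes for everyone who completes treatment. It is not a duration that varies between subjects, and a change score can be negative, which a survival time cannot.

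2. **Event.** The nearest candidate is improvement or worsening in PCS or MCS, in the preceding sentence of section 8.3.3. It is attached to the Mantel-Haenszel test. No number of points is given for either direction, and nothing says whether a change must be confirmed at a later visit.

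3. **Time origin.** None is stated for SF-36. Table 1 places the baseline survey in screening and schedules none at month 1 day 1. Screening, randomisation and first infusion are therefore all possible origins.

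4. **Event time.** Surveys are taken only at visits. No rule says how a change first seen at a visit becomes an event time.

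5. **Censoring.** Section 8.6 excludes imputation and says which analyses include subjects with early discontinuation visits. It does not say how a quality-of-life event time would be censored at discontinuation, death or a missed form.

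6. **Time-to-event endpoints elsewhere.** Section 8.3.2 names four: CKD 4 or 5, eGFR of 15 or below or dialysis, doubling of creatinine, and a 40% fall in eGFR. All are renal, and the SF-36 sentence refers to none of them.

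7. **Whether another SF-36 analysis does the same job.** The t tests, correlations and Wilcoxon tests are one- or two-variable methods. A Mantel-Haenszel test can be stratified, but no strata are named for its SF-36 use and it is not a regression. Appendix 7 holds only the questionnaire. The open-label extension table adds survey visits but no analysis.

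Items 1 to 5 show that the model cannot be fitted to its stated outcome from the text. Item 7 shows that no other planned SF-36 analysis replaces it.

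One covariate needs separate care. Section 1.1 states: "A confirmed renal response is one that has been documented as present at both 12 and 13 months after initiating therapy". Confirmed response is thus known only after randomisation and may itself be affected by treatment.

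**The case against.** The strongest reply is that time to improvement or worsening was meant. The preceding sentence already treats PCS and MCS change as a category, so this reading has a footing in the text, and the fault can fairly be called under-specification as much as a wrong method. That much stands. It does not rescue the sentence: the cut-off, origin and censoring rule are still absent, and the wording describes change over a fixed interval.

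A second reply is that the opening clause hints at quality of life as a predictor. But the sentence names no time-to-event outcome for it to predict, and it ends with change in quality of life as the thing to be explained.

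A third is that the analysis is ancillary and can be tidied before analysis. That is fair, and it limits the severity.

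Some stronger inferences are not supported:

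- A reader might infer that the whole SF-36 plan fails. The t tests, correlations and Wilcoxon tests can be run as written; only the Mantel-Haenszel test of improvement or worsening shares a gap, the cut-off.
- A reader might infer that a time-to-event version would rest only on the few scheduled survey visits. Early discontinuers complete SF-36 at a visit timed from their last dose, and Table 1 (footnote 3) and section 6.2 extend the EOS/ETD assessments to unscheduled visits where indicated.
- A reader might size the problem from the expected responders or evaluable subjects in section 8.5. Those are design assumptions for the primary endpoint and would be the same under any SF-36 model.
- A reader might infer that stepwise selection is itself the error, or that the aim should become an arm comparison. The stated aim is to identify related factors, and the mismatch of model and outcome does not change that aim.

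**Conclusion.** The point holds. The only multivariable SF-36 analysis cannot be carried out as written on its stated outcome, in section 8.3.3 and in the synopsis alike. The missing cut-off also leaves the Mantel-Haenszel test of improvement or worsening incomplete.

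The severity is minor. One ancillary analysis needs its model replaced or its outcome defined, and one test needs a cut-off. The primary and secondary endpoints and the sample size are unaffected. The conclusion rests on the text alone and needs no numerical assumption. It does assume that no separate document, such as an SF-36 analysis manual, supplies the missing definitions; the protocol cites the SF-36 user's manual only for scoring.

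**What to change.** In both places, replace proportional hazards regression with a linear model for PCS and for MCS: ANCOVA of the end-of-treatment score, adjusted for baseline score and the two stratification factors.

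- Name the visit that supplies the end-of-treatment score. The month 12 survey is taken before the twelfth infusion, so the initial EOS visit gives the first score after it.
- Keep treatment arm in the model whatever its p-value.
- List the candidate clinical factors in advance. If stepwise selection is retained, confine it to that list.
- Describe any coefficient for confirmed renal response as an association. When response is in the model, do not present the arm coefficient as the treatment effect.
- Report the number of subjects contributing, since section 8.6 allows no imputation.
- State the change in points that counts as improvement or worsening for the Mantel-Haenszel test.

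If a time-to-event outcome was intended, keep the model and define the event, score cut-off, time origin and censoring rule instead.

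The cost is a short wording amendment in two places, with the IRB/IEC approval that section 12.9 requires, plus routine programming. No new data or visits are needed.

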## 8.2 Analysis of Study Population and Subject Characteristics

Enrollment, major protocol violations, and discontinuations from the study will be summarized. Demographic and baseline characteristics, such as age, sex, race, weight, disease characteristics and markers of organ function at Screening will be summarized using means, standard deviations, medians, ranges for continuous variables, and proportions for categorical variables.

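### Stepwise selection at 5% entry and stay leaves the false-selection rate for SF-36 factors uncontrolled, and cannot show whether contributions are independent or equivalent

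*Combined protocol and SAP*

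**What the plan says.** The SF-36 paragraph of section 8.3.3 and the matching text in the synopsis describe a stepwise proportional hazards regression. Its aim is to determine "whether the QOL measures reflect contributions that were independent of or equivalent to those made by" three things: "treatment assignment, presence or absence of confirmed renal responses, or clinical characteristics". The selection rule is that the "significance level for entry into and for staying in the model set at 5% will be used to identify clinical and health status factors", and the factors sought are those "related to changes in QOL measures from the beginning to the end of treatment".

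The same paragraph introduces the instrument with "The SF-36 assesses 8 scales of health status from which a physical component summary (PCS) and a mental component summary (MCS) are derived". Section 8.2 gives an open list for baseline summaries ("Demographic and baseline characteristics, such as age, sex, race, weight, disease characteristics and markers of organ function at Screening"), but does not tie it to this model.

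The text does not give a list or number of candidates, a variable that always stays in the model, a correction for the number of candidates screened, an interval to be reported, or an equivalence margin. It also gives no rule for interpreting a factor that fails to enter.

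**The concern.** Three features cause trouble, whichever regression family is used.

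- **Unadjusted screening.** Every candidate is tested at 5%, so the chance that at least one enters by luck grows with the size of a list that has not been fixed.
- **Coupling with the outcome.** The rule looks for health-status factors, and the plan describes the SF-36 itself as scales of health status. If baseline scales are offered as candidates for change in the SF-36, they correlate with that change through regression to the mean, even in patients whose health is stable.
- **Wrong tool for the question.** Independence and equivalence concern the size of an adjusted effect and its uncertainty. Passing or failing a 5% threshold in a data-chosen model measures neither, and treatment itself may be absent from the final model.

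At stake is how the plan's only multivariable quality-of-life analysis is read. A factor could be reported as related to SF-36 change, or as independent of treatment, on evidence that does not support it.

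**Working it through.** **Inputs from the plan.** Entry and stay at 5% (8.3.3). Design rates 25% and 55%, 80% power, 18% drop-out, 41 evaluable and 50 randomised per arm (8.5). No imputation (8.6). The number of candidates, k, is not given, so it is varied below.

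**The plan's own figure.** With mean rate 0.40, n per arm = [1.96·√(2·0.40·0.60) + 0.8416·√(0.25·0.75 + 0.55·0.45)]² / 0.30² = (1.358 + 0.555)² / 0.09 = 40.7, so 41. Then 41/0.82 = 50. The sample size reproduces, and about 82 patients is a fair working size for the SF-36 model. Results at 100 are nearly identical.

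**False selection when nothing is related.** For independent candidates and one outcome, P(at least one enters) = 1 − 0.95^k. A full 5%/5% stepwise linear simulation (n = 82, 1,500 runs) agrees and shows the effect of correlation among candidates:

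| k | 1 − 0.95^k | Simulated, corr. 0 | corr. 0.3 | corr. 0.6 |
|---|---|---|---|---|
| 5 | 23% | 23% | 20% | 15% |
| 10 | 40% | 39% | 36% | 25% |
| 14 | 51% | – | – | – |
| 15 | 54% | 55% | 45% | 33% |
| 20 | 64% | 65% | 53% | 36% |
| 24 | 71% | – | – | – |

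A Cox score test at the first step (50% events assumed) gives the same picture: 40%, 52% and 63% for k = 10, 14 and 20 independent candidates. With the 8 SF-36 scales intercorrelated 0.5 plus 2, 6 or 16 independent clinical candidates, the first-step rate is about 32%, 45% and 67%. Treating the physical and mental summaries (PCS, MCS) as two independent outcomes, k = 8 gives 1 − 0.95^16 = 56%.

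**Regression to the mean.** Assume no true change, test-retest correlation r for the summary score, and a baseline scale correlated c with the baseline summary. The correlation of that scale with the change is then −c·√((1 − r)/2). At n = 82 a correlation beyond ±0.217 reaches p < 0.05. The last two columns come from simulation (4,000 runs, first entry step).

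| r | c | Correlation with change | One scale qualifies | At least one of 4 qualifies |
|---|---|---|---|---|
| 0.7 | 0.5 | −0.19 | 42% | 81% |
| 0.7 | 0.8 | −0.31 | 81% | 95% |
| 0.8 | 0.5 | −0.16 | 27% | 66% |
| 0.8 | 0.8 | −0.25 | 63% | 87% |
| 0.9 | 0.5 | −0.11 | 17% | 46% |
| 0.9 | 0.8 | −0.18 | 37% | 62% |

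Allowing for simulation error the range is roughly 45% to 96%. The values of r and c, and the use of 4 scales, are assumptions.

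**Can entry or non-entry settle independence?** Take n = 82, k = 12 and two true contributors, each with slope 0.2 to 0.3 SD and correlated 0.3 to 0.7 with each other. Both are kept in 1% to 46% of runs. Part of this is ordinary lack of power, but it shows that absence from the selected model is weak evidence against an independent contribution.

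**The case against.** The strongest reply is that this is an ancillary factor search on which no trial conclusion depends. Section 8.3.3 also plans separate Mantel-Haenszel tests of improvement or worsening in PCS or MCS against treatment and against confirmed renal response, so a treatment effect is not lost if treatment fails to enter. That stands, and it limits the priority.

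Some stronger readings are tempting, but the documents do not support them.

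- **That the rule names a false factor most of the time.** For one outcome this needs about 14 independent candidates, or about 20 correlated 0.3. The plan gives no count. One can assemble 24 from variables it mentions elsewhere, but none of those lists is assigned to this model. With 5 to 10 candidates the rate is 15% to 40%.
- **That the plan treats non-entry as showing no independent contribution.** No such rule is written. The plan offers selection as the means of answering the question and gives no other criterion; that is as far as the text goes.
- **That the factors named will be mostly noise.** The calculations assume that nothing is related, or that no patient truly changes. They do not give the false share when some factors are real.
- **That stepwise selection causes treatment effects to be missed.** For an assumed 0.5 SD effect at 41 per arm the miss rate is 39%, or 43% with renal response in the model. That is ordinary type II error. A baseline-adjusted fixed model would miss 32% to 41% under the same assumptions.

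It is also fair to say that health status might mean ECOG performance status and NYHA class rather than baseline SF-36 scales. The regression-to-the-mean result is therefore conditional.

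**Conclusion.** The concern holds in a limited form. As written, the rule has a false-selection rate that nothing in the plan controls. The rate is several times the nominal 5% for any plausible list: 15% to 65% across 5 to 20 candidates, depending on their correlation, and 71% for 24 independent ones. If baseline SF-36 scales are candidates, an artefact of measurement error adds to this, with its size resting on the assumed reliabilities and correlations. Whatever the list, passing or failing a 5% threshold cannot establish that a contribution is independent, and equivalence cannot be claimed without a margin. Priority is low to moderate. The primary and secondary endpoints are untouched.

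**What to change.** In section 8.3.3 and the synopsis, replace the stepwise rule with one fixed linear model for end-of-treatment PCS and one for MCS, in place of proportional hazards regression, since no event or event time is defined for a change score.

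- Always include baseline score, treatment and the two randomisation factors, plus a short list of clinical covariates named in advance.
- Fit each model without and then with confirmed renal response, and report the treatment and response coefficients with 95% confidence intervals.
- State that the model containing renal response conditions on a variable observed after randomisation, and so is descriptive.
- Make no statement of equivalence unless a margin is named and the interval lies inside it.
- Label any further search for factors exploratory.

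This changes wording only and uses data already scheduled for collection. The cost is that the covariates must be chosen in advance, so fewer candidate factors are explored.
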